## Randomization and Allocation

Each month of the study, each ICU is assigned to either saline or balanced crystalloids. So that each ICU would experience an equal number of months assigned to saline and balanced crystalloids while minimizing monthly imbalances in the hospital's overall use of each crystalloid, we generated two sequences of study group assignment ([1] saline during odd-numbered months and balanced crystalloid during

even-numbered months; [2] balanced crystalloid during odd-numbered months and saline during even-numbered months) and planned for three ICUs to be assigned to one sequence and the remaining two ICUs to the opposite sequence. To facilitate the early administration of the assigned crystalloid in the ED and operating room prior to the patient's physical arrival in the ICU, a single computer-generated, simple randomization was performed in which the three ICUs that admit the majority of patients from the ED (medical ICU, trauma ICU, and surgical ICU) were randomized 'en bloc' to one sequence of crystalloid group assignments and the two ICUs that admit the majority of patients from the operating room (neurological ICU and cardiac ICU) were randomized 'en bloc' to the opposite sequence of crystalloid group assignments (Figures 1-2).

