### **Statistical Analysis Principles**

All analyses will be performed using R version 3.2.0 (R Foundation for Statistical Computing, Vienna, Austria). To maximize transparency and reproducibility, a complete version of the R code that will be used to analyze the final study data is available in Additional File 1. This ensures that (1) statistical reviewers or external investigators will be able to replicate the pre-specified analysis of the trial independently and (2) any changes or additions to the statistical analysis introduced by investigators or reviewers after completion of enrollment will be evident as differences between the pre-specified code and the analysis code included with the final publication.

All analyses will be conducted at the level of the individual patient during an individual hospitalization in an intention-to-treat fashion unless otherwise specified. Continuous variables will be reported as mean  $\pm$  standard deviation, mean and 95% confidence interval, or median and interquartile range; categorical variables as frequencies and proportions. Between-group comparisons will be made with the Mann-Whitney rank sum test for continuous variables, chi-square test for categorical variables, generalized estimating equations for repeatedly measured variables, and generalized linear mixed-effects models for analyses of the primary and secondary outcomes. A two-sided  $P$  value  $< 0.05$  will be considered to be statistically significant.

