## Primary Analysis

To account for the cluster-level-allocation, cluster-level-crossover structure of the trial, the primary analysis will be an intention-to-treat comparison of the primary outcome of MAKE30 between the saline and balanced crystalloid groups using a generalized linear mixed-effects model including fixed effects (group assignment, age, gender, race, source of admission, mechanical ventilation, vasopressor receipt, diagnosis of sepsis, and diagnosis of traumatic brain injury) and random effects (intensive care unit)[27,28].

In preparation for SMART, we electronically collected the same set of variables that would be used to analyze SMART from the records of all 11,582 patients admitted to the study ICUs between January 1, 2014 and December 31, 2014. With the data on MAKE30 from the 11,582 patients admitted in the year before the trial, using generalized linear mixed-effects modeling treating the five ICUs as clusters and the 12 months as periods, we calculated the intra-cluster correlation coefficient to be 0.142, the intra-period correlation coefficient to be 0.026, and the intra-cluster intra-period correlation coefficient to be  $<0.001$ .

Using the data from the 11,582 patients admitted in the year before the trial, we performed a series of simulated trials evaluating a variety of trial conditions and potential results including: (1) outcome differences between groups ranging from no difference to a 50% relative risk reduction, (2) heterogeneity of treatment effect by cluster, (3) change in the incidence of the outcome in the control group over the course of the trial, (4) varying levels of intra-cluster correlation, and (5) varying levels of intra-period correlation. In each case the generalized linear mixed-effect model appeared to adequately account for the correlation between participants. Analysis using generalized linear mixed-effects modeling and generalized estimating equations accounting for the same variables produced identical odds ratios and 95% confidence intervals for the difference between the simulated groups in the primary outcome.

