## Main Secondary Analysis

Anticipating (1) a wide range in the total volume of crystalloid received by study participants and (2) the potential for greater difference in outcomes between study groups among those patients who receive larger volumes of crystalloid, the main secondary analysis will compare the proportion of patients experiencing MAKE30 in the saline and balanced crystalloid groups, accounting for patients' overall volume of isotonic crystalloid received. For this analysis, we will construct a logistic regression model with MAKE30 as the outcome and independent variables of study group, total isotonic crystalloid received between enrollment and 30 days, and the interaction between the two (as a cross-product term). This will allow us to determine whether any volume of crystalloid receipt exists at which use of balanced crystalloids decreases the risk of MAKE30 compared with saline.

Given that total crystalloid receipt is a variable that emerges after enrollment, we will perform sensitivity analyses (1) using total crystalloid receipt in the 72 hours after enrollment (before incident acute kidney injury or death are likely to have affected isotonic crystalloid administration), (2) replacing the actual total crystalloid receipt with predicted total crystalloid receipt based on a multivariable linear regression model using patient and ICU characteristics available at the time of enrollment derived from crystalloid administration in the study ICUs in the year prior to the trial, and (3) comparing outcomes between study groups among a "modified intention-to-treat" population of patients who received at least 500 mL of any study crystalloid in the 72 hours after enrollment.

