## Additional Secondary Analyses

We will perform the following additional secondary analyses:

- (1) Comparison of secondary outcomes between study groups.
- (2) Effect modification by severity of illness and pre-specified subgroups. Using generalized linear mixed effects modeling, we will examine the interaction between crystalloid assignment and the following baseline variables with respect to the primary outcome of MAKE30 in the intention-to-treat population:

- a. Source of admission to the ICU (Emergency department, Operating room, Transfer from another hospital, Hospital ward, Other)
- b. Study ICU (Medical, Surgical, Cardiac, Neurological, Trauma). [Because cluster cannot be treated as a random effect for this subgroup, we will use logistic regression modeling]
- c. Sepsis or septic shock (Yes, No)
- d. Traumatic brain injury (Yes, No)
- e. Receipt of mechanical ventilation (Yes, No)
- f. Receipt of vasopressors (Yes, No)
- g. Category of renal dysfunction at the time of enrollment (No renal dysfunction, Acute kidney injury, Chronic kidney disease, End-stage renal disease receiving RRT)
- h. Risk of in-hospital mortality as predicted by baseline University HealthSystem Consortium expected in-hospital mortality (continuous variable ranging 0.0 to 1.0)

(3) Sensitivity analysis excluding patients admitted in the week prior to a crossover ('washout'). We will repeat the primary analysis comparing MAKE30 between study groups in the intention to treat population excluding those admitted in the 7 days prior to a crossover in ICU crystalloid assignment (simulating a "washout" period). Prior data from the study ICUs suggests that less than 10% of patients remain in the ICU for longer than 7 days[14]. Excluding those admitted within 7 days of a crossover in ICU crystalloid assignment will allow use of a baseline factor to exclude the majority of patients who would go on to experience a crossover in crystalloid assignment due to the study design.

(4) Sensitivity analysis excluding patients who were transferred between ICUs or remained in the ICU through a crossover ('per protocol'). We will repeat the primary analysis comparing MAKE30 between study groups in the intention to treat population excluding those who remained in the intensive care unit through a crossover in crystalloid assignment or were transferred between study ICUs.

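### The main secondary analysis is a plain logistic model with no ICU or baseline term and no rule for searching across volumes, and, like the primary model, it has no month term

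*Combined protocol and SAP*

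**What the plan says.** The SAP section Main Secondary Analysis (repeated in the 6/15/17 protocol and the published plan) lists three independent variables in a logistic regression for MAKE30: study group, "total isotonic crystalloid received between enrollment and 30 days, and the interaction between the two (as a cross-product term". The model is meant to show "whether any volume of crystalloid receipt exists at which use of balanced crystalloids decreases the risk of MAKE30".

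Other sections bear on this:

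- Statistical Analysis Principles provides for "generalized linear mixed-effects models for analyses of the primary and secondary outcomes", with a general two-sided 0.05.
- Primary Analysis defines that model: eight baseline covariates and a random effect for ICU. It has no month term. The same section reports "the intra-period correlation coefficient to be 0.026" from the year before the trial.
- Additional Secondary Analyses departs from the mixed model once, for the study-ICU subgroup, and says why: "Because cluster cannot be treated as a random effect for this subgroup, we will use logistic regression modeling".
- Corrections for multiple testing labels only the additional secondary analyses as hypothesis-generating. The status of the main secondary analysis is not stated.
- Main Secondary Analysis acknowledges that volume arises after enrollment and plans three sensitivity analyses. One replaces received volume with volume predicted "using patient and ICU characteristics available at the time of enrollment".
- Under Randomization and Allocation, the ICUs fed mainly by the emergency department take one sequence and those fed mainly by the operating room are assigned "to the opposite sequence of crystalloid group assignments".

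**The concern.** There are two separate gaps.

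**Model terms.** The written model omits the ICU and baseline terms that the SAP's general rule would bring in, with no stated reason. A calendar-month term is missing from both this model and the primary model. Three ICUs run against two, of unequal size, and the medical ICU enrolls alone at first. A good or bad month therefore does not fall equally on the two groups.

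**The question asked.** Looking along a fitted line for any volume at which balanced fluid helps is a search. The general 0.05 does not say which test answers it or how looking at many volumes is controlled.

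At stake is a statement that balanced fluid lowers risk above some number of litres. It could be made too often under no effect. It could also be read as a randomised comparison, although received volume is not fixed at enrollment.

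**Working it through.** **1. The plan's own figure.** With 7,000 per group and 15.0% against 13.1%, the standard error is √[(0.15×0.85 + 0.131×0.869)/7000] = 0.00587. Then 0.019/0.00587 − 1.96 = 1.28, which gives power of 89.9%. The stated 90% reproduces. It concerns the primary analysis; no figure is given for the main secondary analysis.

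**2. Variance components.** I take 0.142 and 0.026 on the latent logit scale (an assumption). The total is 3.290/(1 − 0.142 − 0.026) = 3.954. The ICU variance is 0.142 × 3.954 = 0.561 (SD 0.75) and the month variance 0.026 × 3.954 = 0.103 (SD 0.32).

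**3. Sampling variance of the group log odds ratio.** 2/(7000 × 0.15 × 0.85) = 0.00224.

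**4. Month shocks, equal arms per ICU.** A month effect enters the group contrast with weight d: the balanced group's share of patients in that month minus the saline group's share. I assume 22/18/16/14/12 months for the medical, neurological, cardiac, trauma and surgical ICUs (82 unit-months), all ending April 2017. Annual sizes are from Figure 12B of the 2015 protocol (2,300, 1,212, 1,892, 1,693, 2,126). Each group then has 75,951 size-weighted units.

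- 4 months, medical alone: 2,300/75,951 = 0.0303
- 2 months, medical against neurological: 1,088/75,951 = 0.0143
- 2 months, cardiac added: 804/75,951 = 0.0106
- 2 months, trauma added: 889/75,951 = 0.0117
- 12 months, all five: 3,015/75,951 = 0.0397

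The sum of d² is 0.0235. Results under no treatment effect:

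- Independent months at 0.026: added variance 0.103 × 0.0235 = 0.00241; standard error understated by √(1 + 0.00241/0.00224) = 1.44; false-positive rate 2Φ(−1.96/1.44) = 17%.
- Independent months at 0.005: month variance 0.0193, factor 1.10, rate 7%.
- Smooth annual cycle with the 0.026 variance: consecutive months carry opposite signs of d and nearly cancel; rate about 5%.
- No month effect: 5%. ICU shares are equal between groups, so an ICU term changes nothing here.

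**5. Odd month counts.** June 2015 to April 2017 is 23 months, and SAP Figure 1 shows 23 medical entries, which cannot split equally. I assume 23/19/17/12/11 (also 82). The ICU share differences are −0.0242, 0.0186, 0.0286, 0.0023 and −0.0253, with sum of squares 0.00240. The added variance is 0.561 × 0.00240 = 0.00135, the factor 1.27 and the rate 12% with no month effect. An ICU term removes this part.

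**6. Simulation of the volume model.** Setting: 14,000 patients, 15% MAKE30, no effect. Volume was assumed lognormal with 8% receiving none and about a quarter receiving more than 4 L. There were 300 to 1,500 runs per case (Monte Carlo error about 1 to 2 points).

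| Model, independent months at 0.026 | Group effect at a given volume |
|---|---|
| As written | 17-19% at 4 L |
| With ICU, or ICU and baseline | 15-20% |
| With ICU, baseline and month | 4-6% |

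With a smooth cycle or no month effect, the model as written gives about 5% under equal arms and about 10-15% under odd counts. The received-volume interaction test stayed at 2-7% in every case, because a month effect shifts risk at all volumes alike.

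**7. The search across volumes.** For a straight-line interaction, the chance that some volume passes a pointwise 0.05 test is at most P(χ² on 2 df > 3.84) = exp(−1.92) = 14.6% in either direction, or 7.3% in one, even with a correct model. Over 0-10 L, the model as written favours balanced fluid somewhere in about 5-14%, against 2.5%. With the added terms and a simultaneous limit (|z| > √5.99 = 2.448), this is 1-2%.

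**8. Predicted volume.** Predicted volume uses ICU characteristics, and the two blocs of ICUs run on opposite sequences. Its interaction test can therefore pick up month differences. At independent 0.026 without a month term it gives 10% or 22% if emergency-fed ICUs give 1.35 or 1.8 times the volume of the others (assumed ratios). With the month term it gives 5%.

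**The case against.** The strongest reply has four parts.

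- **Rule.** The section on this analysis is specific, and a specific provision may override a general sentence. A reader might also infer that omitting month breaches the mixed-model rule. It does not: the SAP's own mixed model has no month term. The rule supports only the ICU and baseline terms, which under equal arms do not lower the error rate.
- **Size.** The SAP Discussion speaks of seasonal change and trends and calls the period effect small. The reported 0.026 is compatible with a smooth pattern and no inflation. This stands. The documents state no pattern, so 17-19% is one end of a range.
- **The sponsor's simulations.** These varied intra-period correlation, and the SAP reports: "In each case the generalized linear mixed-effect model appeared to adequately account for the correlation between participants". That concerns the mixed model. No error rates are given, and the text does not say whether a period term was included. It does not cover the plain logistic volume model.
- **Already handled.** A reader might infer that the plan overlooks the post-enrollment nature of volume, or that its interaction test is invalid. Neither is supported. The plan names the problem and pre-specifies three sensitivity analyses, and the interaction test on received volume holds its level. How prominently to show the predicted-volume version is a matter of presentation.

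The R code cited in Statistical Analysis Principles is not in the documents and may already contain some of these terms.

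**Conclusion.** The point holds in a limited form and should be addressed. The model text and the general mixed-model sentence conflict without explanation, the search across volumes has no rule, and the analysis's status is unstated. These three rest on the text alone. The missing month term is a gap in both the main secondary and the primary model, not a breach of the SAP's rule.

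The inflation affects the group effect at a given volume, not the received-volume interaction. Its size depends on the unknown month pattern and on the schedule; Figure 1's lower rows are damaged in the available text, so the exact schedule is uncertain. The volume distribution, the latent-scale reading of the correlations and the pointwise search over 0-10 L are assumptions. Confidence is medium.

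**What to change.** - Fit the main secondary model with the primary model's ICU random effect and baseline covariates, plus a calendar-month term (random intercept or indicators). Use the same ICU and month terms in the planned predicted-volume analysis.
- Name the interaction coefficient as the test. Show volume-specific odds ratios with a simultaneous 95% band over a stated volume range.
- Reconcile Statistical Analysis Principles with Main Secondary Analysis, and state this analysis's status beside Corrections for multiple testing.
- Do not present an effect at a given received volume as a randomised comparison.

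No new data are needed. By simulation, the standard error of the group effect at 4 L grows by 12-13% with month indicators or 2-10% with a random intercept; that of the interaction grows by about 1% or less. Part of the loss arises because months with only the medical ICU enrolling (before 1 October 2015) carry no within-month comparison under month indicators. If the R code already contains these terms, only the text needs correcting.

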## Additional Secondary Analyses

We will perform the following additional secondary analyses:

- (1) Comparison of secondary outcomes between study groups.
- (2) Effect modification by severity of illness and pre-specified subgroups. Using generalized linear mixed effects modeling, we will examine the interaction between crystalloid assignment and the following baseline variables with respect to the primary outcome of MAKE30 in the intention-to-treat population:

- a. Source of admission to the ICU (Emergency department, Operating room, Transfer from another hospital, Hospital ward, Other)
- b. Study ICU (Medical, Surgical, Cardiac, Neurological, Trauma). [Because cluster cannot be treated as a random effect for this subgroup, we will use logistic regression modeling]
- c. Sepsis or septic shock (Yes, No)
- d. Traumatic brain injury (Yes, No)
- e. Receipt of mechanical ventilation (Yes, No)
- f. Receipt of vasopressors (Yes, No)
- g. Category of renal dysfunction at the time of enrollment (No renal dysfunction, Acute kidney injury, Chronic kidney disease, End-stage renal disease receiving RRT)
- h. Risk of in-hospital mortality as predicted by baseline University HealthSystem Consortium expected in-hospital mortality (continuous variable ranging 0.0 to 1.0)

(3) Sensitivity analysis excluding patients admitted in the week prior to a crossover ('washout'). We will repeat the primary analysis comparing MAKE30 between study groups in the intention to treat population excluding those admitted in the 7 days prior to a crossover in ICU crystalloid assignment (simulating a "washout" period). Prior data from the study ICUs suggests that less than 10% of patients remain in the ICU for longer than 7 days[14]. Excluding those admitted within 7 days of a crossover in ICU crystalloid assignment will allow use of a baseline factor to exclude the majority of patients who would go on to experience a crossover in crystalloid assignment due to the study design.

(4) Sensitivity analysis excluding patients who were transferred between ICUs or remained in the ICU through a crossover ('per protocol'). We will repeat the primary analysis comparing MAKE30 between study groups in the intention to treat population excluding those who remained in the intensive care unit through a crossover in crystalloid assignment or were transferred between study ICUs.

(5) Sensitivity analysis including only each patient's first admission to a participating intensive care unit during the study period. We will repeat the primary analysis

comparing MAKE30 between study groups in the intention to treat population including only the first ICU admission in the study for each patient.

### **Corrections for multiple testing**

All of the additional secondary analyses will be considered hypothesis-generating and no corrections for multiple comparisons will be performed.

### **Handling of Missing Data**

Of the components of the MAKE30 primary outcome, data regarding in-hospital mortality and receipt of new renal replacement therapy are not anticipated to be missing for any patients[14,22]. In contrast, the persistent renal dysfunction component of MAKE30 may suffer from missing data for serum creatinine value at baseline or between enrollment and hospital discharge. In a pilot study of 974 patients in the same hospital, 31 patients (3.2%) had no measured serum creatinine between enrollment and hospital discharge[14]. Of these 31 patients, 6 (19.4%) died within hours of ICU admission and qualified for the MAKE30 outcome via the in-hospital mortality criteria. The remaining 25 (80.6%) were low acuity ICU patients with a normal creatinine value measured in the 24 hours prior to ICU admission who were discharged from the hospital within 48 hours without another serum creatinine measurement. Of these, 24 had a subsequent outpatient serum creatinine value measured in the next 90 days, all of which were in the normal range. Thus, patients without a serum creatinine measurement between enrollment and hospital discharge, who do not experience in-hospital mortality or new RRT, will be classified as having not experienced the MAKE30 outcome.

With regard to missing data for baseline serum creatinine, in the same pilot study 595 of 974 patients (61.0%) had a measured serum creatinine value between 12 months and 24 hours prior to hospital admission[14]. Of those without such a measurement, 259 of 379 (68.3%) had a value measured between 24 hours prior to hospital admission and study enrollment. Only 120 of 974 patients (12.3%) did not have an available serum creatinine value prior to enrollment. For the main analysis, patients without a measured serum creatinine value between 12 months prior to hospital

admission and enrollment will have a baseline creatinine value estimated using a previously-described three-variable formula[29]. Multiple alternative approaches to missing baseline creatinine data will be explored in sensitivity analyses including use of complete cases, multivariable single imputation, and use of the first creatinine after enrollment or the highest or lowest creatinine during the study (see Appendix 5).

